### ***Viral Shedding Assessments***

Viral shedding will be assessed during the study treatment period before the drug administration and also during the follow-up period.

Urine samples, saliva samples, and stool samples will be taken on the days as specified in [Table 9.5-1](#), [Table 9.5-2](#), and [Table 9.5-3](#). Samples will be measured for virus genome copies by qPCR. In addition, viral shedding samples may be analyzed in an exploratory method that assess infectivity and the results may be reported separately.

[REDACTED]

## **9.9 Health Economics OR Medical Resource Utilization and Health Economics**

Health Economics/Medical Resource Utilization and Health Economics parameters will not be evaluated in this study.

## **10 STATISTICAL CONSIDERATIONS**

### **10.1 Sample Size Determination**

#### **10.1.1 Dose Escalation**

##### **10.1.1.1 Monotherapy Dose Escalation (Part 1)**

Dose escalation during the BMS-986277 monotherapy dose escalation (Part 1) will be guided by BLRM employing the Escalation With Overdose Control (EWOC) principle. The BLRM method is fully adaptive, makes use of all the information available at the time of each dose assignment, not just data from the current dose level, and directly addresses the ethical need to control the probability of overdosing. Furthermore, the BLRM uses the knowledge gained from participants treated with enadenotucirev. The targeted toxicity rate in this study is in the range of [16%, 33%]. The boundary is similar to the toxicity boundary used by a rule-based design (ie, 3 + 3 design) in that a minimum is set to 16% (approximately 1 in 6) DLT rate and a maximum at 33% (approximately 2 in 6) DLT rate. The use of the EWOC principle limits the risk of exposing participants in the next cohort to an intolerable dose by ensuring the posterior probability of the DLT rate exceeding 33% at any dose is capped at 35%.

Due to the nature of the dose escalation process, the exact number of participants to be treated at each dose level cannot be precisely determined. The maximum number of participants to be treated is approximately 24. However, simulation studies with various scenarios show that the expected number of DLT-evaluable participants is no more than approximately 18 ([Appendix 9](#)). Additional participants (up to a total of 12) may be treated at any dose level to further evaluate the safety, PK, and/or pharmacodynamics profile. The total sample size is up to 72.

Approximately 3 participants will be treated at the starting dose levels of BMS-986277. While the BLRM will use DLT information from the DLT period only, clinical assessment will take into consideration the totality of available data, including PK/pharmacodynamics from all treated participants in assigning a dose level for the next cohort of 3 participants. At least 6 DLT-evaluable participants will be treated at a dose level before it can be recommended as the BLRM-RD for BMS-986277 monotherapy.

The BLRM-RD for BMS-986277 monotherapy is the dose that satisfies the following 3 conditions:

- 1) The empirical posterior probability that the “DLT rate of 16% to < 33%” is greater than a pre-specified value (ie, 50%);
- 2) This probability needs to be the largest among the dose levels that satisfy the EWOC condition (ie, the probability that the “DLT rate  $\geq$  33%” must be no greater than 35%);
- 3) A minimum number of participants (ie, 6) was treated at this dose level.

The final RD for BMS-986277 monotherapy will be based on the recommendations from the BLRM and overall clinical assessment of all available safety, PK, pharmacodynamic, and efficacy data. Lower doses of BMS-986277 may be tested if none of the planned doses are found to be tolerable as monotherapy. Such decisions will be made after discussion and agreement between the investigators and the BMS Medical Monitor (or designee).

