### **Stopping Rules:**

The following are the general stopping rules of BLRM during monotherapy dose escalation:

- If all of 24 DLT-evaluable participants are treated.
- If all of the current prespecified doses are considered intolerable according to the prespecified cutoff (ie, EWOC criteria), then the model will recommend stopping the current dose level and a new dose level lower than the current lowest dose level can be identified.
- The maximum number of DLT-evaluable participants in a dose level will be 12. This limit is set to avoid instances in which the model could recommend adding subjects indefinitely to a specific dose level due to uncertainty in the tolerability profile.
- If, for a specific dose level, 6 subjects have been treated and the chance of determining that the dose level to be the “target” dose is  $> 50\%$ , then the model will suggest to stop and declare the current dose level to be the BLRM-recommended dose (BLRM-RD).

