### **BLRM-RD:**

The BLRM-RD is the dose that satisfies the following 3 conditions:

- 1) The empirical posterior probability that the ‘DLT rate of 16% to  $< 33\%$ ’ is greater than 50%,
- 2) This probability needs to be the largest among the dose levels that satisfy the EWOC condition (ie, the probability that ‘DLT rate  $\geq 33\%$ ’ must be no greater than 35%);
- 3) Minimum number of participants (ie, 6), were treated at this dose level.

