## **2.2 Simulation Parameters**

Simulation study was done for monotherapy dose escalation using various hypothetical scenarios. One thousand trial simulations were used for each scenario. All simulations were run using EAST 6.3.1® software BLRM module for BMS-986277 monotherapy. The number of participants to be

treated in each cohort in a specific dose level, the stopping rules used to identify the BLRM-RD, and other simulation parameters are defined as:

- Fixed cohort size: 3
- Probability of overdosing:  $\leq 35\%$
- Target probability of toxicity: 0.33, the upper boundary of the targeted toxicity interval
- Probability of achieving the target toxicity:  $> 50\%$
- Maximum number of participants treated: 24
- Prior specification on model parameters:
  - Mean:  $\log(\alpha_1) = -0.959$ ,  $\log(\beta_1) = 0.884$
  - Variance:  $\log(\alpha_1) = 1.010$ ,  $\log(\beta_1) = 1.537$
  - Correlation: 0.055
- Posterior sampling method: Metropolis Hastings
- Minimum number of participants treated at a given dose level in order to identify the BLRM-RD: 6
- Maximum number of participants at a dose: 12

The provisional dose levels for BMS-986277 monotherapy are  $3 \times 10^{10}$ ,  $3 \times 10^{11}$ ,  $1 \times 10^{12}$ , and  $3 \times 10^{12}$  vp, with  $3 \times 10^{12}$  as the reference dose (dose expected to have 30% DLT).

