**Table 3: Simulation Results of BLRM for Monotherapy**

Scenario	BMS-986277 Dose	3x10 	3x10 	1x10 	3x10 	MTD not Selected (%)	Fitted Median MTD	Avg Toxicity Observed (%)	Avg # Pts
By prior	% DLT	0	0	3	28				
	% MTD	0.0	0.0	50.7	49.3	0.0	3.2x10 	11.0	18.3
	# Pts	3.0	3.0	9.5	6.7				
	# DLTs	0.0	0.0	0.3	1.9				
Flatter than the one by the prior	% DLT	5	10	15	25				
	% MTD	0.3	4.2	62.8	32.3	0.4	3.1x10 	16.0	16.4
	# Pts	3.1	4.7	9.0	6.7				
	# DLTs	0.2	0.5	1.4	1.7				
Narrow safety window	% DLT	0	2	5	50				
	% MTD	0.0	0.0	85.8	14.2	0.0	2.9x10 	13.9	18.2
	# Pts	3	3.4	11.3	4.6				
	# DLTs	0.0	0.1	0.6	2.3				
All low	% DLT	0	0	0	10				
	% MTD	0.0	0.0	11.0	89.0	0.0	3.6x10 	5.5	18.6
	# Pts	3.0	3.0	6.5	10.0				
	# DLTs	0.0	0.0	0.0	1.0				
All within	% DLT	16	21	27	32				
	% MTD	6.5	22.9	54.8	10.7	5.1	1.9x10 	25.5	14.5
	# Pts	3.8	5.5	8.0	5.4				
	# DLTs	0.6	1.1	2.2	1.8				

Note: Bolded numbers are doses with true target toxicity within the target toxicity interval [16%, 33%]

Note: % DLT, true DLT rate; % MTD, proportion of the dose selected as the MTD; # Pts, average number of pts given the dose was tried; # DLTs, average number of DLTs given the dose was tried; Fitted MTD: fitted MTD at 33% as the target toxicity rate; % toxicity observed, average proportion of DLTs given the doses were tried

Abbreviation: Avg = average; NA = not applicable; Pts = participants.

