The average sample size was no more than approximately 18 participants. Most scenarios have a fitted median MTD that is close to the reference dose and the  $1 \times 10^{12}$  vp dose was chosen as the MTD most frequently in all scenarios except the all low scenario. These results demonstrate how the EWOC principle limits the risk of exposing participants from a toxic dose level, where only the all low would select  $3 \times 10^{12}$  vp as the MTD most frequently. The prior parameters derived from the enadenotucerv DLT data suggests the selected doses are all relatively safe, with the DLT rate at  $3 \times 10^{12}$  vp artificially increased to allow for the potential increase in DLT due to the mechanism of activating T cells. This results in the  $1 \times 10^{12}$  vp dose selected as the MTD approximately 50% of the time. If, however, emerging data suggests the  $1 \times 10^{12}$  vp dose is relatively safe, the model will still allow  $3 \times 10^{12}$  vp to be selected as the MTD and this occurs approximately 50% of the time as well. This nicely illustrates the EWOC principle. The model performs well in the flatter than prior and all within scenarios by correctly identifying the MTD within the target toxicity interval, [16%, 33%) about 95% of the time and performs adequately by the prior scenario. Overall, the scenarios illustrated above demonstrate that the model performs satisfactorily in the hypothetical scenarios investigated by correctly identifying the MTD while limiting participants from receiving excessive/unacceptable toxic dose levels.

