### Interpretation and Use of [Figure 2](#):

[figure not shown]
Figure 2 is a snapshot of stacking histogram with DLT information available at dose level  $3 \times 10^{10}$  vp and  $3 \times 10^{11}$  vp. This figure will be updated each time new DLT information becomes available.

When recommending the next dose level, the model will first exclude doses that are intolerable (with overdosing probabilities > 35%, the rate that has been specified for BMS-986277). Among those qualified candidate doses that are considered “tolerable”, the model will select the dose that maximizes the probability of being within the target toxicity range (DLT rate between 16% and 33%). However, there will be no dose skipping during the dose escalation monotherapy phase of the study.

As illustrated in Figure 2, the distribution of predicted DLT rates will be characterized into possibilities falling into 3 different categories. First, dose levels  $3 \times 10^{12}$  vp for BMS-986277 are excluded according to the higher-than-cutoff overdosing probabilities (0.579 for  $3 \times 10^{12}$  vp). Among the remainder of tolerable dose levels, the BLRM recommends the dose that maximizes the probability of being within the target dosing interval. Therefore, the model’s recommendation would be to stay at  $1 \times 10^{12}$  vp, which is associated with the highest target dosing probability of 0.418 compared with that of  $3 \times 10^{10}$  vp (0.068) and  $3 \times 10^{11}$  vp (0.254).

Similarly (although not shown on Figure 2), according to the rules specified above, the model could possibly recommend to de-escalate to a lower dose level than the current treated dose level, escalate to the next dose level, or even recommend to stop and identify a new dose level lower than  $3 \times 10^{10}$  vp, the lowest pre-specified dose level. Please refer to the description of [Figure 1](#) for details on how to specify the new dose levels.

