**3.1 Example of using the BLRM for BMS-986277 Monotherapy Dose Escalation**

[figure not shown]
According to safety consideration and clinical judgement, the dose level  $3 \times 10^{10}$  vp is recommended as the starting dose for BMS-986277 monotherapy. With the current BMS-986277 prior specified in the Section 1.2 and all available DLT information up to  $3 \times 10^{12}$  vp, a

corresponding decision tree illustrating various models' recommendations under all possible scenarios for the first two cohorts is provided in Figure 4.

Tracing a branch of the decision tree in Figure 4 illustrates the decision making process. Taking the left-most branch of the tree as an example, starting at  $3 \times 10^{10}$  vp, if there were 0 DLTs observed in the real clinical trial, the model would recommend to escalate to  $3 \times 10^{11}$  vp (the BLRM actually recommends escalating to the highest dose  $3 \times 10^{12}$  vp, but since this is a 100-fold increase of dose and dose skipping is not allowed, the dose level  $3 \times 10^{11}$  vp is selected), one level above the current treated dose level according to the escalation rules per protocol. Next, if there is 0 DLTs observed at  $3 \times 10^{11}$  vp, the model would recommend to escalate further to  $1 \times 10^{12}$  vp. At  $1 \times 10^{12}$  vp, there would be 3 potential decisions (0/3 escalate, 1/3 and 2/3 would stay, and 3/3 would de-escalate); this is not shown due to crowding the diagram.

During the actual clinical study, the tree would be narrowed or deepened based on actual DLTs observed. The clinical team will be able to leverage this decision tree to preview decisions at each interim monitoring step and to plan proactively.

**Figure 4: The BLRM Model Hypothetical Decision Tree for BMS-986277 Monotherapy during Dose Escalation (for the first 2 cohorts)**

Abbreviations: DE = de-escalation; E = escalation; S = stay.

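### Table 3's dose selections, and the conclusion drawn from them, cannot come from the written BLRM-RD definition with its 50% target-probability condition

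*Protocol*

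**What the plan says.** Protocol 10.1.1.1 sets three conditions for the monotherapy BLRM-RD. The first is that the posterior probability of a DLT rate from 16% to below 33% "is greater than a pre-specified value (ie, 50" per cent). The second is that this probability is the largest among doses whose probability of a DLT rate of 33% or more is at most 35%. The third is at least 6 participants at the dose. Appendix 9 section 2.1 repeats them ("The BLRM-RD is the dose that satisfies the following 3 conditions"), and so does SAP 6.1.

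The stopping rules in Appendix 9 section 2.1 cap enrolment at 12 DLT-evaluable participants per dose and 24 in total. Once 6 are treated at a dose with target probability above 50%, "the model will suggest to stop and declare the current dose level to be the BLRM-recommended dose". The only other outcome described is that all doses are intolerable, in which case a lower dose can be sought.

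Section 2.2 introduces its list of settings as including "the stopping rules used to identify the BLRM-RD". That list contains the above-50% condition, the minimum of 6, and the caps of 12 and 24. Table 3 then shows a dose selected in 94.9% to 100% of trials; its column "MTD not Selected" runs from 0.0% to 5.1%. The text below it says an in-range MTD is identified about 95% of the time in two scenarios, and that "the model performs satisfactorily in the hypothetical scenarios investigated by correctly identifying the MTD".

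**The concern.** When few DLTs occur, the posterior for a dose sits mostly below 16%, so its target probability is low. A dose with a true DLT rate of 0% to 5% should then rarely, if ever, pass a 50% condition. Table 3 nevertheless selects 1×10¹² vp often in scenarios where its true rate is 0%, 3% or 5%, and almost never reports that no dose was selected.

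If the selections come from a different rule, the stated operating characteristics do not belong to the definition that investigators, ethics committees and regulators are reading. At stake is the accuracy of the performance claims supporting the escalation design, not the safety of its dosing rule.

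**Working it through.** **Inputs.** Prior from Appendix 9 section 2.2: means (−0.959, 0.884), variances (1.010, 1.537), correlation 0.055 for (log α, log β). Model: logit(p) = log α + β·log(dose / 3×10¹²). Caps, cohort size 3 and conditions as above. True DLT rates from Table 3. The posterior was computed by numerical integration on a grid.

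**Anchor to the protocol's own example** (0/3 at 3×10¹⁰, 1/3 at 3×10¹¹; Figure 2 text):

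| Quantity | Protocol | Recomputed |
|---|---|---|
| P(target), three lower doses | 0.068 / 0.254 / 0.418 | 0.068 / 0.257 / 0.415 |
| P(overdose), 3×10¹² | 0.579 | 0.561 |

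Agreement is within 2 percentage points. The 95% claim is also traceable: Table 3 gives 62.8 + 32.3 = 95.1% for Flatter (counting the 15% dose as in range, as the table does) and 6.5 + 22.9 + 54.8 + 10.7 = 94.9% for All within.

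**What it takes to name 1×10¹².** Take every allocation in cohorts of 3 with total at most 24 and at least 6 at 1×10¹², no DLT at lower doses, and any result at 3×10¹². The largest P(target) at 1×10¹² is:

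- 0.061 with 0 DLTs at that dose
- 0.388 with 1
- 0.557 with 2

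So at least 2 DLTs there, or a DLT at a lower dose, are needed. The 50/50 mixture of the Table 2 components gives 0.029, 0.383 and 0.570, so the requirement is the same.

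**Ceilings for 1×10¹².** At most 12 participants are treated per dose, so binomial tails with n = 12 bound the selection share whatever the escalation path, overdose limit or skipping rule:

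- By prior (3% there, 0% below): 1 − 0.97¹² − 12(0.03)(0.97¹¹) = 4.9%
- All low (0% there and below): 0%
- Narrow (5% there, 2% at 3×10¹¹, 0% at 3×10¹⁰): P(at least 2 of 12 at 5%) = 11.8%; P(no DLT in 12 at 2%) = 0.98¹² = 0.785; either route: 1 − (1 − 0.118)(0.785) = 31%

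**Ceiling for 3×10¹² in All low.** With no DLTs below and 3 at each lower dose, P(target) at 3×10¹² is 0.168 after 0/12, 0.358 after 1/12 and 0.536 after 2/12. The largest value found with at most one DLT is 0.491, at 1/6. Two DLTs are therefore needed: 1 − 0.9¹² − 12(0.1)(0.9¹¹) = 34.1%. The lower doses cannot qualify, having no DLTs, so at least 100 − 34.1 = 65.9% of trials have no BLRM-RD.

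Because 1/6 is a near miss, suppose it did pass. The ceiling becomes (1 − 0.9⁶) + 0.9⁶ × P(at least 2 of 6 at 10%) = 0.469 + 0.531 × 0.114 = 53%, still far from 89.0%.

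| Scenario, dose | Ceiling under the definition | Table 3 |
|---|---|---|
| By prior, 1×10¹² | 4.9% | 50.7% |
| All low, 1×10¹² | 0% | 11.0% |
| Narrow, 1×10¹² | 31% | 85.8% |
| All low, 3×10¹² | 34% | 89.0% |
| All low, none (floor) | 66% | 0.0% |

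With 1,000 simulations the standard error near 50% is √(0.5 × 0.5 / 1000) = 1.6 points, so these are not simulation noise.

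**Sensitivity results only.** Enumerating all trial paths gives the share with no qualifying dose. Ranges cover skipping on or off.

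| Overdose limit | By prior | Flatter | All within | Narrow | All low |
|---|---|---|---|---|---|
| 0.35 throughout | 80–85% | 49–58% | 20–25% | 92–96% | 82–86% |
| 0.40 for escalation, 0.35 in the definition | 56–62% | 34–43% | 15–23% | 86–89% | 70–73% |
| 0.40 throughout | 45–47% | 31–34% | 13–17% | 79% | 70% |
| Table 3 | 0.0% | 0.4% | 5.1% | 0.0% | 0.0% |

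These move because one common state, 0/3 at each of the three lower doses, has overdose probability 0.3488 at 3×10¹². The limit the software effectively applied is also uncertain: section 3.1 says that after 0/3 at the start "the BLRM actually recommends escalating to the highest dose", whereas the recomputed overdose probability there is 0.392, above 0.35.

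**The case against.** The strongest reply is that Table 3 reports an MTD, not a BLRM-RD, that its notes refer to a fitted MTD at 33%, and that a redacted block just before it may state the software's selection rule. This does not remove the mismatch. Section 2.2 lists the 50% condition among the rules for identifying the BLRM-RD, and the definition itself is unredacted. Hidden text giving another rule would confirm that Table 3 describes something else.

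A reader might infer that Part 1 could end with no route to a recommended dose. The documents do not support that. Protocol 7.1.4.1 and 10.1.1.1 and the final-dose paragraph of Appendix 9 section 2.1 base the RD on model output plus overall clinical assessment; 10.1.1.2 sets the Part 2 starting dose relative to the RD; and the Figure 1 text allows intermediate doses. What the BLRM-RD is when a cap is reached with no dose above 50% is left unsaid, but that is mainly missing detail. Nor is exposure at issue, because the overdose limit works independently of the 50% condition.

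A reader might also quote the 80–85% in By prior as the failure rate. It depends on the effective overdose limit and falls to 45–47% at 0.40. In Narrow and All low no dose is truly on target, so naming none is correct there; it is simply not what the table shows.

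Finally, one might conclude that Table 3 used the next-dose rule in the Figure 2 text, under which "the model will select the dose that maximizes the probability of being within the target toxicity range". Choosing the best admissible dose at the cap does match the not-selected column (0.0/0.1/0.0/0.0/4.3% against 0.0/0.4/0.0/0.0/5.1%). At 0.35 with skipping, however, one such version splits By prior 78/22 between the two top doses, against 51/49. The rule behind Table 3 is not identified.

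**Conclusion.** The point holds: Table 3 and the performance statements beneath it cannot describe the written BLRM-RD definition. The firm evidence is the set of ceilings: 4.9%, 0% and 31% for 1×10¹² against 50.7%, 11.0% and 85.8%, and about 34% for 3×10¹² in All low against 89.0%. They assume the section 2.2 prior, the standard two-parameter logistic form, and the caps of 12 and 24. They do not depend on the overdose limit or dose skipping. The All low figure for 3×10¹² rests on a narrower margin (0.491 against 0.50), but even conceding it leaves 53% against 89.0%.

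The 95% claim concerns Flatter and All within, where only sensitivity results are available. Across the variants run, the definition names any dose at all in at most 100 − 31 = 69% and 100 − 13 = 87% of trials respectively.

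This is a should-fix matter of stated operating characteristics. It does not bear on how the final RD is chosen, on overdose control, or on the doses participants receive.

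**What to change.** Choose one rule, re-run Table 3 under it without dose skipping and at the 35% limit, and rewrite the paragraph after the table to match. Two options:

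- **(a)** Use the above-50% condition only as the early-stop trigger. At the caps, define the BLRM-RD as the dose with at least 6 participants, within the overdose limit, that has the highest target probability.
- **(b)** Keep the definition and add to Table 3 the share of trials with no BLRM-RD. The stated performance will be less favourable.

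Align SAP 6.1 with the choice. Its narrative also gives a 25% overdose cap beside the 35% in its condition 2, so one limit should be stated. Appendix 9 section 5.1 repeats the 50% condition for the combination, so Table 8 deserves the same check; it was not recomputed here because the copula formula is redacted.

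The cost is a clarifying sentence in each document and a simulation re-run, with no additional participants.

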#### **10.1.1.2 Combination Dose Escalation (Part 2)**

The dose level for BMS-986277 in combination with nivolumab will be determined based on the RD for BMS-986277 monotherapy established in Part 1, the BLRM-copula RD with nivolumab monotherapy, and incorporating knowledge gained from participants treated with enadenotucirev in combination with PD-1 inhibitor (nivolumab or pembrolizumab). The starting dose for BMS-986277 in combination with nivolumab will be 1 dose level below the RD.

Initially, approximately 3 participants will be treated at this dose level and escalation will be guided by BLRM-copula. While the BLRM-copula will use DLT information from the DLT period only, clinical assessment will take into consideration the totality of available data, including PK/pharmacodynamics from all treated participants in assigning a dose level for the next cohort of 3 participants. At least 6 DLT-evaluable participants will be treated at a dose level before it can be recommended as the BLRM-copula RD for BMS-986277 in combination with nivolumab. Additional participants (up to a total of 12) may be treated at any dose combination below or at the BLRM-copula RD for further evaluation of safety, PK, or pharmacodynamic parameters as required. A combination with a lower, intermediate, or higher dose level of BMS-986277 may be considered if the BLRM-copula recommends it, after consideration of all available safety, PK, and pharmacodynamic data. The total sample size in this part is up to 36.

The final RP2D for BMS-986277 in combination with nivolumab will be based on the recommendations from the BLRM-copula and overall clinical assessment of all available safety, PK, pharmacodynamic, and efficacy data. This final RP2D will be used in the cohort expansion.

